7.9.4 Abnormal imaging outcome showing suspicion of pancreatic cancer

For abnormal MRI imaging outcomes showing suspicion of pancreatic cancer, it is standard of care to perform a follow up CT scan to evaluate resectability (staging CT scan), and endoscopic ultra sound scans (EUS) depending on the local HPB multidisciplinary team (MDT). Therefore, for any abnormal MRIs showing suspicion for cancer a contrast staging CT scan will be ordered by the local HPB centre according to NICE guidelines G18. Standard of care CT and MRI imaging reports will be provided as clinical study data, which will be assessed according to NCNN guidelines v1 2023 and will inform on resectability status. Decisions about resectability status will be determined by the local HPB multidisciplinary team (MDT). To determine resectability for the study endpoint, the MRI and CT scans will be reviewed by the multidisciplinary study team (MDST) and will neither influence patient care nor be fed back to the local MDT team.

Table 1. Definition of borderline resectable pancreatic cancer as assessed by contrast CT pancreas protocol.

	Feature	Requirement
Resectable	a. Normal tissue plane between tumour and vessels b. No evidence of metastatic disease.	a and b
Borderline resectable	a. Loss of normal tissue plane between tumour and vessels. b. Venous involvement (contact and or distortion) of the (Superior Mesenteric Vein) SMV, (Portal Vein) PV or SMV-PV confluence – allowing surgical reconstruction. c. Tumour abutment <180° of the (Superior Mesenteric Artery) SMA or coeliac axis. d. No evidence of metastatic disease.	a and/or b or c and d
Unresectable	a. Encasement/contact of SMA or coeliac axis of >180°. b. Long segment involvement/occlusion of the SMV, PV or SMV-PV confluence with no reconstruction possible. c. Encasement of the hepatic artery. d. Confirmed metastatic disease.	one or more of a, b, c, d.

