 - Sensitivity of Avantect test for detecting PC – number of individuals in the intervention arm with one or more Avantect “detected” test results and PC divided by the number of individuals in the intervention arm with PC.
 - Specificity of Avantect test for ruling out PC – number of individuals in the intervention arm with no Avantect “detected” test results, at least one Avantect “not detected” test result and no diagnosis of PC divided by the number of individuals in the intervention arm with no diagnosis of PC.
 - Resectability rate – number of individuals with PC deemed resectable by the study multidisciplinary team (MDT) divided by the number of PCs.

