7.6.4 Timepoint T3 (2 years after T2)

T3 refers to the three years of follow-up (following recruitment at T0) which will be collected via linkage with the cancer and mortality registry. At the time of writing the cancer registry is managed by the National Cancer Registration and Analysis Service which sits within NHS England, and the mortality register is managed by the Office for National Statistics but can be accessed through NHS England. Cancer and mortality registry data will still be required and sought even if the owner of the dataset changes in the future. A cancer and mortality registry download will be obtained on three

occasions: once 6,400 participants have been recruited, once 15,000 participants have been recruited, and at 3 years post last participant recruited.

Data Collection from Cancer Registry:

- Any cancer diagnosis (ICD10 C00-D48)
- Date of cancer diagnosis
- Site of cancer diagnosis
- Stage of cancer at diagnosis
- Histology of cancer
- Survival status
- Cancer treatments

Data Collection from Mortality Registry:

[figure not shown]
- Date of death
- Causes of death

The local site study team will collect and keep NHS number, address and contact details (including 1 or 2 phone numbers and an email address) from all participants. NHS numbers and dates of birth for all participants will be shared securely by site to the SCTU. SCTU will then pass on the NHS numbers and dates of birth to the administrators at the registries to allow them to perform registry searches on three occasions during the study. The local site team will also share with the SCTU study team, via secure email, the contact details (name, postal and email address) for a select number of participants (numbers to be defined) who have consented to optional further research questionnaire.

Addresses will be used by sites to contact participants with any Avantect “Detected” results by post. Phone numbers will be used by sites to contact participants if required throughout the study, including contacting participants to inform them of a “Detected” Avantect test if deemed more appropriate than by post alone (at the discretion of the clinical team).

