7.9.2 Abnormal imaging outcome

Participants referred for imaging who have abnormal imaging results will be returned to routine clinical care (via local HPB team) for further clinical management as per current NHS practice.

If pancreatic cancer, other solid pancreatic lesion or other cancer type is identified based on imaging and biopsy is performed then de-identified imaging reports and any subsequent de-identified biopsy or resection pathology reports will be collected as part of the study clinical data. Participant would discontinue further study blood collections. Diagnoses will be based on reports of pathologic evaluation performed at the treating institute. Digital Imaging and Communication in Medicine

(DICOM) images will be obtained and reviewed at the end of the study phase as a quality control measure. If cyst fluid is sampled the de-identified cytology and any cyst fluid chemistry lab reports will be obtained and included in study data.

If imaging is abnormal and no biopsy or surgery is planned, de-identified imaging reports will be provided as part of study data and the cancer and mortality registry searches will be completed as planned. Participants with abnormal imaging results (suggestive of cancer) will discontinue further blood collection, but cancer and mortality registry searches will be completed as planned.

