9.2 SAMPLE SIZE

Upon conclusion of the pilot, further recruitment to the study will occur with a planned interim analysis for futility and efficacy. Participants in the pilot study will continue to have their data analysed. The planned interim analysis is referred to as ‘stage 1’ analysis for convenience. The final analysis is referred to as ‘stage 2’ analysis. In each stage, there are three co-primary endpoints:

1. sensitivity (of the Avantect test),
2. specificity (of the Avantect test) and

3. resectability of diagnosed PCs

In the stage 1 interim analysis, these endpoints will be assessed within the intervention arm, as more information will be available on the diagnostic status of this group. In the stage 2 final analysis, the sensitivity and specificity of the test will be estimated within the intervention arm, whereas resectability will be compared between the arms.

The anticipated prevalence of a pancreatic cancer diagnosis within 3-years of follow-up within this population is 1%³. Conservative estimates place the anticipated sensitivity of the Avantect test at 65% sensitivity and 95% specificity in the detection of PC. Under usual care in the UK, 10-20%^{13,14} of pancreatic cancer patients receive surgery with curative intent due to the majority (80%) presenting at Stage III or Stage IV¹⁵. Data from the CAPS cohort¹⁶ in the US has demonstrated that it is possible to reduce the proportion of patients presenting with late stage disease if surveillance testing is conducted on at-risk subgroups, thus improving the availability of curative resection as a treatment strategy. It is hoped that the Avantect test can improve the resectability of pancreatic cancers from a rate of 14% in usual care to 40% in the intervention arm (just over a 2.5-fold increase).

With three co-primary endpoints, each endpoint must be reached for an overall successful result. To achieve an overall power of 90%, the power for each endpoint should be $90\%^{(1/3)} = 96.5\%$. Following guidance from Korevaar and colleagues¹⁷, the analysis will consist of a one-sided test at an cumulative alpha of 0.05 at the final analysis. Because there is an interim analysis at stage 1 for efficacy and futility, the one-sided significance level changes at the interim and final analysis.

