Two of the three co-primaries are metrics of test accuracy. In practice test results will not be available for all participants due to machine failure, insufficient blood sample quality, shipping or processing, or participants being unable to provide a blood sample. To reduce the number of participants where no test results are available, three collection time points are included. In the case where a blood draw did not occur or the sample was not analysable following a scheduled visit, a repeat blood draw will be arranged. The expected proportion of participants who are expected to not have a single Avantect result is 2.5%.

Using the PropTestPower function in the R package EnvStats, it was determined that 73 individuals with pancreatic cancer are required in each arm to detect a change of resectability from 14% in usual care to 40% in the intervention arm. At the stage 2 final analysis, allowing for interim analysis, the overall power would be 96.5%. Allowing for 2.5% loss to arrive at the Per Protocol population (see section 9.4), this increases to 75 cases per arm (150 total), which at an event rate of 1% leads to a recruitment target of 7,500 per arm (15,000 total). As only samples from the intervention arm are to

be tested for the purpose of the analysis, with an anticipated test sensitivity of 65% and specificity of 95%, this leads to the following confusion matrix in the intervention per protocol group (7,312):

		Diagnostic status	
		Has PC diagnosis	Does not have PC diagnosis
Avantect test result	Detected	48	362
	Not detected	25	6,877

With 73 cases of pancreatic cancer of which $48/73 = 65\%$ were detected by the Avantect test, this would be sufficient to rule out a sensitivity lower than 42 % in the stage 2 final analysis at 96.5% power. On discussion with the FDA, a specificity of 92% would be considered acceptable within this clinical context. With 6,877 individuals without a pancreatic cancer diagnosis of which $6,877/7,239 = 95\%$ are expected to be detected by the Avantect test, more than 99% power is achieved to rule out a specificity lower than 92%.

Definition of ‘promising result’ in study stage 1 to guide progression to study stage 2

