At the stage 1 interim analysis, co-primaries will be considered ‘futile’, ‘promising’ or ‘efficacious’ according to the following table:

	Expected proportion	Futility threshold at stage 1	Promising result range at stage 1	Efficacy threshold at stage 1
Sensitivity	65%	<46.5%	46.5% to 63.1%	>63.1%
Specificity	95%	<92.0%	92.0% to 94.9%	>94.9%
Resectability	40%	<21.0%	21.0% to 38.1%	>38.1%

At the stage 2 final analysis, the sensitivity co-primary will be considered successful if a sensitivity of 49% can be ruled out with a one-sided p-value of 0.03 among participants in the intervention arm. Specificity will be considered successful if a specificity of 92% can be ruled out with a one-sided p-value of 0.03 among participants in the intervention arm. Resectability will be considered successful if the resectability rate in the intervention arm is higher than the rate in the control arm at a one-sided p-value of 0.03.

Secondary outcomes, in order of importance, are defined as follows, which all are calculated with a minimum of 90% power:

Stage shift - The analysis will be conducted by comparing the proportion of PC cases diagnosed at stage I/II vs III/IV between the intervention and control arms. A proportion of 60% (44/73 PCs) is expected in the intervention arm versus 35% (26/73 PCs) in the control arm, which provides 90% power at a one-sided alpha of 0.05. Stage shift will be considered successful if the proportion in the intervention arm is higher than the rate in the control arm at a one-sided p-value of 0.05.

PPV in detecting PC - The analysis will be conducted within the intervention arm. With a sample size of 7,500, PC prevalence of 1%, and 2.5% lost from the per protocol population, there will be an expected 410 individuals with an Avantect “detected - abnormal” result. 11.6% (48/410) are expected to have a PC. PPV will be considered successful if a null PPV of 5% can be ruled out at a one-sided p-value of 0.05.

NPV in ruling out PC - The analysis will be conducted within the intervention arm with a sample size of 7,500, PC prevalence of 1%, and 2.5% lost from the per protocol population, will be an expected 6,902 individuals without an Avantect “detected - abnormal” result. 99.6% (6,877/6,902) are expected to not have a diagnosis of PC. NPV will be considered successful if a null NPV of 99% can be ruled out at a one-sided p-value of 0.05.

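### The protocol states no route by which resectability, the only co-primary compared between arms, would be read for control-arm cancers or for cancers the test missed.

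*Protocol*

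**What the plan says.** **The endpoint.** Protocol section 2.2 defines the resectability rate as "number of individuals with PC deemed resectable by the study multidisciplinary team (MDT) divided by the number of PCs". The denominator is all pancreatic cancers, not only those found through the test. Section 9.2 says that at the final analysis sensitivity and specificity are estimated within the intervention arm, "whereas resectability will be compared between the arms". Section 9.4 calls it a success if the intervention rate is higher than the rate "in the control arm at a one-sided p-value of 0.03".

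**How it is scored.** Section 7.9.4 leaves the clinical decision to the local HPB team and gives the endpoint to the study's own team: "To determine resectability for the study endpoint, the MRI and CT scans will be reviewed by the multidisciplinary study team (MDST". Table 1 in that section classifies cancers by vessel planes, degrees of arterial contact and metastatic disease, assessed on contrast CT.

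**Where scans come from.** Section 7.8.1 arranges pancreas imaging for intervention-arm participants with a detected result. Section 7.9.2, which sets out the collection of reports and DICOM images, begins: "Participants referred for imaging who have abnormal imaging results will be returned to routine clinical care". Not-detected participants carry on with scheduled visits (7.8.2), and controls receive usual diabetes care (synopsis).

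**How other cancers are found.** Section 7.6.4 collects follow-up by linkage to the cancer and mortality registries. The closest cancer registry field to resectability is "Stage of cancer at diagnosis". The others are diagnosis, date, site, histology, survival status and treatments.

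**The concern.** An endpoint that compares two randomised arms needs the same measurement, from the same kind of source, in both. Here the measurement is a reading of scans, and the protocol describes obtaining scans on a pathway that control participants never enter.

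This endpoint drives the recruitment target of 15,000 and is the only co-primary that rests on randomisation. Section 9.2 requires all three co-primaries to succeed. If the reading is missing for most or all control cancers, the analysis must either drop them, impute a status, or take one from another source. Each option can produce or hide an arm difference unrelated to any effect of the test. A statistical analysis plan cannot repair this, because it cannot analyse images that were never requested.

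**Working it through.** **1. Reproduce the design figure.** Inputs from section 9.2: 73 cancers per arm, and a sample chosen "to detect a change of resectability from 14% in usual care to 40% in the intervention arm". The text adds that "the overall power would be 96.5" per cent. The one-sided level of 0.03 is from section 9.4.

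- Pooled rate = (0.14 + 0.40)/2 = 0.27; SE under the null = √(0.27 × 0.73 × 2/73) = 0.0735.
- SE under the alternative = √(0.14 × 0.86/73 + 0.40 × 0.60/73) = 0.0703.
- Power = Φ[(0.26 − 1.881 × 0.0735)/0.0703] = Φ(1.733) = 95.8%.

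This is within one point of the stated figure, so the design holds if all 73 + 73 cancers are scored.

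**2. Count the cancers with a stated route to a reading.** Section 9.2's confusion matrix has 48 detected and 25 not detected among 73 intervention-arm cancers; 73 are expected in the control arm.

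| Group | Expected cancers | Stated route to scans |
|---|---|---|
| Intervention, detected | 48 | Yes (7.8.1, 7.9.2, 7.9.4) |
| Intervention, not detected | 25 | None found |
| Control | 73 | None found |

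Without a stated route: (25 + 73)/146 = 98/146 = 67%. The 48 is an upper limit. Some detected participants may decline imaging (7.8.1) or have normal imaging (7.9.1) and be diagnosed later. Section 7.9.2 mentions DICOM images in the paragraph on biopsied cases, and only reports where no biopsy or surgery is planned.

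**3. Check the other data sources.**
- Registry fields (7.6.4): no images and no resectability.
- Health record review (7.1): selected pre-existing conditions, at T0 to T2 only.
- The clause in 7.11 that collects imaging when available names no arm, but it concerns cancers unrelated to the pancreas and incidental findings.
- The MDST's remit (13.4) is study-related scans.

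**4. Illustrations of the consequence.** The protocol states no rule for unread cancers, so each case rests on an assumption named here.

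*(a) Unread counted as not resectable; true rate 14% in both arms.* Control is 0/73. Intervention is X/73, with X ~ Bin(48, 0.14) and mean 6.7. One-sided Fisher against 0/73 gives p = 0.060 for X = 4 and p = 0.029 for X = 5, so success at 0.03 needs X ≥ 5. P(X ≥ 5) = 0.82. The false-success rate is about 82% against a nominal 3%.

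*(b) Only read cancers analysed, with no selection bias.* With 48 intervention cancers read and an assumed fraction of the 73 control cancers read, the formula in step 1 (with unequal group sizes) gives:

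| Control cancers read | Power |
|---|---|
| 25% | 56% |
| 50% | 79% |
| 75% | 87% |
| 100% | 91% |

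*(c) Selection bias when only detected cancers are read.* Take the arm's true rate as 40% (0.40 × 73 = 29.2 cancers) and assume missed cancers are resectable at 14% (0.14 × 25 = 3.5). The detected-only rate is (29.2 − 3.5)/48 = 54%, against a true 40%.

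**The case against.** The strongest reply is that nothing in the protocol says scans are collected only after a detected result. The heading of 7.8 is limited to the intervention arm, but that of 7.9 is not. Section 7.9.4 says, without naming an arm, that standard-of-care imaging reports will be provided as study data. Section 2.2 defines the endpoint over all cancers, and section 16.3 lists hospital records and radiographs among source documents. The intention may be that the MDST reads every cancer. The trial schema and the result-management schema in 7.7 are also not visible in the text available, and the Data Management Plan is a separate document.

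Part of this stands. The restriction is inferred from the structure of 7.8 and 7.9 and from the absence of any other route, and a route could exist in a document not shown. But 7.9 continues from the detected pathway, 7.9.5 ties imaging to the T0, T1 and T2 tests, reports are not the scans the MDST is to read, and the source-data list is generic. Intending to read every cancer does not say how a control participant's scans are obtained. The data source of a co-primary belongs in the protocol.

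It is also fair to say that the protocol nowhere proposes to score unread cancers as not resectable or to infer resectability from registry treatment. Actual resection is a separate secondary endpoint, and section 9.4 assumes that 5% of resectable cancers will not be resected.

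**Conclusion.** The concern holds as a missing data source. For about 98 of 146 expected cancers (67%), including every control-arm cancer, the protocol states no route to the reading that defines the endpoint. The count rests on section 9.2's expected figures and on all 48 detected cancers being imaged, so it is approximate.

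A reader might infer two stronger things. The first is that control cancers cannot be scored at all. The text supports only that no route is stated: staging scans made in routine care may exist and could be requested. The second is that the trial would win automatically. That depends on a scoring rule the protocol does not contain, and even then success needs at least five resectable intervention cancers, reached in about 82% of trials at a true rate of 14% in both arms. The 82%, the power losses and the 54% are illustrations of what an unsettled rule could do, not predictions.

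This should be settled before control-arm cancers accrue, because the comparison that sizes the trial depends on it.

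**What to change.** Amend sections 7.6.4, 7.9.2 and 7.9.4 as follows.

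- For every pancreatic cancer in either arm, however identified, request from the treating centre the staging CT/MRI (as DICOM, whether or not a biopsy was done) and the documented local MDT resectability status at diagnosis.
- The MDST reads all scans masked to arm and to Avantect result.
- The primary comparison uses the MDST reading in both arms, and scan availability is reported by arm.
- Cancers without a reading are not counted as not resectable by default.
- Local MDT status is not substituted case by case in the primary analysis. Scans are likely to be missing more often in the control arm, so substitution would restore the imbalance of source. Use local status for all cancers in both arms as a sensitivity analysis.

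**Cost.** About 100 further existing scan sets to retrieve. Some will be requested retrospectively, because control cancers surface at three registry downloads, and some will come from hospitals with no role in the study. Added reading time for the MDST, a protocol amendment and a check that the consent wording covers retrieval are also needed. There is no new procedure for participants and no change to their care.

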7.5 BLINDING AND PROCEDURES FOR UNBLINDING

7.5.1 Blinding

After the T0 visit, participants will be randomised to either intervention or control arm as described in 7.4. Participants will remain blinded to their allocation unless the condition stated in section 7.5.2 is met.

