7.8 AVANTECT OUTCOMES AND FOLLOW UP FOR PARTICIPANTS IN THE INTERVENTIONAL ARM

7.8.1. Detected

The CI will request the SAFE-D site team to notify participants in the intervention arm with Avantect “detected” test results and their GPs of the result via letter and an optional phone call (at the discretion of the clinical study team). The CI will also request the site team to arrange an urgent suspected cancer referral (tumour specific pathway referral) to local hepatobiliary (HPB) service Local Collaborator for a pancreas MRI (or CT if MRI is contraindicated) and imaging will be scheduled as per standard of care for suspected cancer pathway.

If participant with Avantect “detected” test result is unable or unwilling to undergo imaging of pancreas, participant will be removed from further Avantect testing, but will be included in the analysis and any cancer and mortality registry searches.

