9.3 STUDY TIMEPOINTS

There will be three timepoints for blood collection: at baseline (T0), 6 months +/- 2 weeks post-baseline (T1), and 12 months +/- 2 weeks from baseline (T2). For each study timepoint, the Avantect test will be conducted. For samples collected from participants assigned to the intervention arm, the Avantect test will be assessed as soon as possible within 14 business days of receipt of samples in the analysing laboratory at ClearNote Health. Those with positive test results (test result = Avantect “detected”) in the intervention arm will undergo diagnostic pancreas imaging. Samples collected from participants assigned to the Control arm will be stored for potential future Avantect testing or future research.

The study design comprises a pilot and two study stages:

- Stage 1 Analysis will be carried out 6 months after the T1 visit for 3,200 participants in the intervention arm. Only participants followed up for a minimum of 6 months after the T1 visit in the intervention arm will be included in this analysis.
- Stage 2 Analysis will be carried out after 3-year follow-up data has been collected for all 15,000 participants.

In addition, during the study annual readouts will be provided to the data monitoring committee to monitor study progress and inform on decisions to continue or stop the study.

The diagnostic performance of the Avantect test results will be summarised according to the pancreatic cancer diagnoses collected by the point of analysis. The stage shift, and resection rate of pancreatic cancer will be summarised by arm. For this purpose, a positive test at any timepoint will be considered a ‘positive prediction’ e.g., if a participant has a negative result at T0, but a positive result at T1, their overall prediction will be considered as at-risk of pancreatic cancer.

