13.4 THE SAFE-D MULTIDISCIPLINARY STUDY TEAM (MDST)

The multidisciplinary study team will include a pancreatic surgeon and a radiologist with experience in interpreting pancreatic scans.

The MDST is responsible for verifying all study related imaging scans to provide standardized quality assurance. The MDST will meet quarterly and generate a report of their findings. MDST will not interfere with the local HPB outcome or management plans (unless a significant finding can provide useful information to the patient care).

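### Resectability, the only co-primary compared between arms, is read from MRI as well as CT by a study team that the protocol does not mask to arm

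*Protocol*

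**What the plan says.** - **The comparison.** Section 9.2 estimates sensitivity and specificity within the intervention arm at the final analysis, "whereas resectability will be compared between the arms". Section 9.4 calls resectability successful if the intervention rate exceeds the control rate at a one-sided p-value of 0.03.
- **Who judges it.** Section 2.2 defines the rate as "number of individuals with PC deemed resectable by the study multidisciplinary team (MDT) divided by the number of PCs". Section 7.9.4 separates the local team's decision, which guides care, from the endpoint read: "To determine resectability for the study endpoint, the MRI and CT scans will be reviewed by the multidisciplinary study team (MDST".
- **What the categories rest on.** The caption of Table 1 in section 7.9.4 reads "Definition of borderline resectable pancreatic cancer as assessed by contrast CT pancreas protocol".
- **Who gets study-ordered imaging.** Section 7.8.1 refers participants with a 'detected' result "for a pancreas MRI (or CT if MRI is contraindicated". Section 9.3 says that those with positive results "in the intervention arm will undergo diagnostic pancreas imaging". The synopsis gives the control arm usual diabetes care.
- **Who is blinded.** The trial is called single blind. Section 7.5.1 states: "Participants will remain blinded to their allocation unless the condition stated in section 7.5.2 is met". Section 7.6.1 adds that GPs are blinded at first. Masking of the multidisciplinary study team (MDST) is not mentioned.
- **What else the MDST does.** Section 13.4: "The MDST is responsible for verifying all study related imaging scans to provide standardized quality assurance". No order is given for the quality review and the endpoint read.

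**The concern.** Two things in the endpoint read depend on arm. The first is the file: a study-ordered MRI can be present only for a 'detected' intervention-arm case, so a reader who finds one can often guess the allocation. The second is the modality: the categories are defined on contrast CT, but the endpoint sentence puts MRI and CT before the readers, so many intervention-arm cancers may be scored on more or different images than control-arm cancers. Several Table 1 features call for judgement, such as loss of the tissue plane or whether a vein can be reconstructed.

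This is the one co-primary whose interpretation rests on randomisation. If the read differs by arm, a positive result could be put down to the reading, and a true effect could be diluted. An unmasked read cannot be repaired in the analysis, and the MDST meets quarterly during the study.

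**Working it through.** **Inputs from the protocol.** 73 pancreatic cancers per arm; resectability 14% (usual care) and 40% (intervention); stated power 96.5%; expected 'detected' cancers in the intervention arm 48 of 73 (all section 9.2). Final criterion: one-sided p of 0.03 (section 9.4).

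**Step 1: the plan's own figure.** With pooled rate p̄ = (0.14 + 0.40)/2 = 0.27:
- null standard error = √(2 × 0.27 × 0.73/73) = 0.0735
- alternative standard error = √((0.14 × 0.86 + 0.40 × 0.60)/73) = 0.0703
- power = Φ((0.26 − 1.881 × 0.0735)/0.0703) = Φ(1.73) = 95.9%

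Exact enumeration of the two binomials with the pooled score test gives 96.2%. The stated 96.5% is therefore reproduced closely and is not in dispute.

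**Step 2: how many reads matter.** A rate of 14% is about 10 of 73. Setting 20/73 against 10/73, the pooled rate is 30/146 = 0.2055 and Z = 0.1370/√(2 × 0.2055 × 0.7945/73) = 2.05, above 1.881. At 19/73, Z = 1.87, just short. Ten extra 'resectable' reads are enough for success. Section 9.4 also mentions a one-sided 98.5% interval; at 0.015 it takes eleven.

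**Step 3: no true effect, upward shift.** Assume 14% are truly resectable in both arms, equally among detected and undetected cancers. A share u of the non-resectable cancers on the MRI pathway is called resectable because of the read. That pathway holds 48 × 0.86 ≈ 41 such cancers. The intervention rate becomes 0.14 + 0.86 × (48/73) × u. Exact enumeration, 73 per arm, pooled score test, one-sided 0.03:

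| u | Reads shifted | Intervention rate | Chance of false success |
|---|---|---|---|
| 0 | 0 | 14.0% | 3.0% |
| 5% | about 2 | 16.8% | 7.9% |
| 10% | about 4 | 19.7% | 16.5% |
| 15% | about 6 | 22.5% | 28.8% |

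**Step 4: true effect, downward shift.** Assume true rates of 40% and 14%, and that a share d of the resectable MRI-pathway cancers (48 × 0.40 ≈ 19) is called unresectable, for example because MRI shows disease that CT does not. The intervention rate becomes 0.40 × (1 − (48/73) × d):

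| d | Intervention rate | Power |
|---|---|---|
| 0 | 40.0% | 96% |
| 10% | 37.4% | 93% |
| 20% | 34.7% | 87% |
| 30% | 32.1% | 78% |

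**Step 5: do comparable scans reach the readers?** Section 7.9.2 collects imaging and pathology reports in the context of participants referred for imaging. Section 7.6.4 lists the registry items, and these include neither scans nor resectability. No route is stated by which the CT of a control-arm or 'not detected' cancer reaches the MDST. If a share of control cancers has no readable scan and is counted as not resectable, then with a true 14% in both arms the chance of false success is 5.2%, 8.6% or 13.7% for a share of 10%, 20% or 30% (same test; the shares are assumptions).

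**The case against.** The strongest reply is that the protocol already limits the problem. Section 7.9.4 has a contrast staging CT follow any MRI suspicious for cancer, describes that CT as the scan for evaluating resectability, and sets structured criteria with angles and metastatic status. The protocol does not say that the MDST is unmasked; an imaging charter or the SAP might mask it. The shift rates are assumptions that nothing in the documents supports. All of that stands. It does not remove the point, because the protocol itself fixes which images decide the endpoint, includes MRI among them, and says who is blinded without naming the MDST.

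Three stronger readings are tempting and not supported:
- *An MRI identifies the arm.* Only study-ordered MRI is confined to the 'detected' pathway. Usual care may include MRI, and section 7.9.4 itself mentions standard-of-care MRI reports. Some 'detected' cases have CT only. About 25 of 73 intervention-arm cancers are expected to be 'not detected' and would look like controls.
- *Every intervention-arm cancer is open to the shift.* Applying the upgrade to all of them would give 11.9% and 29.4% at 5% and 10%, but the mechanism reaches only the 48 of 73 on the MRI pathway.
- *Control-arm scans will never reach the readers.* The protocol states no route for them; it does not say there is none.

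**Conclusion.** The point holds as a weakness in how the main between-arm endpoint is assessed, and it should be fixed. The endpoint sentence and Table 1 name different modalities and need reconciling in any case. Followed as written, readers whom the protocol does not mask score files whose content partly depends on arm. This affects up to about 48 of 73 intervention-arm cancers.

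On the assumed shifts, about two to six reads raise the false-success chance for this endpoint from 3.0% to between 7.9% and 28.8%, and the reverse shift lowers power from 96% to between 93% and 78%. These figures illustrate how sensitive the comparison is to a few reads; they do not predict the bias or its direction. They rest on 73 cancers per arm, the 0.03 criterion treated as a single final test, the same true resectability in detected and undetected cancers, and the study MDT of section 2.2 being the MDST of section 7.9.4. They concern this co-primary alone; overall success also needs sensitivity and specificity.

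**What to change.** In sections 7.9.4 and 13.4, state that:
1. The primary endpoint read uses the contrast staging CT on which Table 1 is defined.
2. Files are prepared with arm, Avantect result, referral route, local team decision and treatment removed, and both arms are mixed in each batch.
3. The read is recorded and locked before the MDST sees any MRI, including for quality review. A read of MRI plus CT is kept as a sensitivity analysis.
4. The existing diagnostic staging CT is requested for every pancreatic cancer in both arms, including control-arm and 'not detected' cancers found through the registry.
5. A stated rule says how cancers without a readable CT are counted, identically in both arms.

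This changes endpoint assessment only and asks for no additional imaging. The MDST and its quarterly meeting already exist. The cost is protocol wording and some work for the trials unit in retrieving and masking files, of which retrieval from treating centres is the larger part. The scientific price is that MRI information is left out of the main read.
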